11.5.2 Secondary Efficacy Endpoint(s)

For secondary endpoints, unless otherwise noted, the Chi-squared test will be used for categorical endpoints, the t-test for continuous endpoints, and Log-rank test for time-to-event endpoints. In comparison of means, the Satterthwaite t-test may be used when variances between the two groups are different. These tests will evaluate etanercept monotherapy vs methotrexate monotherapy and etanercept and methotrexate combination therapy vs methotrexate monotherapy.

Proportion of subjects achieving SDAI remission at week 48 for the etanercept plus methotrexate treatment arm will be compared to that of the methotrexate monotherapy arm using the chi-squared test and will be presented with nominal p-values only (eg, no adjustment for multiplicity will be done). To parallel the the primary analysis of the primary estimand, the proportion of subjects in the etanercept plus methotrexate treatment arm and the methotrexate monotherapy arm achieving SDAI remission at week 48 will be evaluated using non-responder imputation, as observed data, and multiple imputation.

The proportion of subjects achieving SDAI remission (≤ 3.3), SDAI continuous score, and SDAI change from baseline at all visits will be summarized by treatment group using the PAS. Subjects with missing SDAI value at week 48 and subjects who disease-worsened are considered non-responders.

DAS28-ESR, DAS28-CRP, and CDAI, and their changes from baseline will also be summarized by visit for each treatment group using the PAS. Missing data will not be imputed for these continuous endpoints. T-tests will compare means between etanercept vs methotrexate and etanercept + methotrexate vs methotrexate.

Proportion of subjects achieving Boolean remission will be tabulated by visit for each treatment group using the PAS. Boolean remission using 28-joint-count, 28-joint-count + feet and ankles, and 66/68 joint count will be assessed.

Proportion of subjects with Disease-Worsening and time-to-disease-worsening will be evaluated by treatment group for the PAS. Time-to-disease-worsening will be evaluated using Kaplan-Meier (KM) curves, estimates, and 95% CIs by treatment group. For subjects with more than one DW Date, the first DW date will be used. Subjects who do not experience disease-worsening will be censored at last SDAI assessment date. In addition, a two-sided log-rank test will evaluate the etanercept monotherapy vs methotrexate monotherapy arms, and the etanercept plus methotrexate combination vs methotrexate monotherapy arms.

Time-to-recapture observed SDAI remission from Rescue Date will be evaluated for the Rescue Analysis Set using Kaplan-Meier (KM) curves, estimates, and 95% confidence intervals by treatment group; subjects who do not recapture SDAI remission will be censored at their last SDAI assessment date. This analysis will be repeated for Time-to-recapture SDAI remission from Disease-Worsening Date for the Disease-Worsening Analysis Set. For subjects with more than one recapture of observed SDAI remission, the first recapture date will be used. Additionally, the proportion of subjects who recapture observed SDAI remission at week 48 will be summarized for both the Rescue Analysis Set and the Disease-Worsening Analysis Set.

Table 1. Primary and Secondary Endpoints Summary Table

Endpoint	Primary Analysis Method	Sensitivity/Exploratory Analysis
Primary Endpoint		
SDAI remission (≤ 3.3) at week 48 as defined by SDAI_remission_maintenance detailed in Section 6.2	
Count (percentage) of subjects achieving SDAI remission as defined by SDAI_remission_maintenance detailed in Section 6.2 at Week 48 for the PAS.
 
A chi-squared test comparing etanercept monotherapy and methotrexate monotherapy using the PAS.
 
Subjects who have a missing SDAI_remission value will be considered as non-responders.
	
Observed_SDAI_remission using as observed approach as detailed in Section 6.5 (missing data will be excluded).
 
Multiple imputation method: impute SDAI values when missing and after rescue for randomized subjects. The composite SDAI values will be imputed rather than its components.

Secondary Endpoints		
SDAI remission (≤ 3.3) at week 48	
Count (percentage) of subjects achieving SDAI remission as defined by SDAI_remission_maintenance detailed in Section 6.2 at Week 48 for the PAS.
 
A chi-squared test comparing etanercept plus methotrexate combination arm and methotrexate monotherapy using the PAS.
 
Subjects who have a missing SDAI_remission value will be considered as non-responders. Nominal p-values will be provided.
	
Observed_SDAI_remission using as observed approach as detailed in Section 6.5 (missing data will be excluded).
 
Multiple imputation method: impute SDAI values when missing and after rescue for randomized subjects. The composite SDAI values will be imputed rather than its components.

SDAI score and change from baseline at all measured timepoints	
Summary statistics for SDAI score and change from baseline at each Analysis Visit for the PAS.
 
T-test comparing etanercept monotherapy vs methotrexate monotherapy
 
T-test comparing etanercept and methotrexate combination therapy vs methotrexate monotherapy
	
DAS28-ESR and change from baseline at all measured timepoints	
Similar analysis as for SDAI score and change from baseline at all measured timepoints
	

Table 1. Primary and Secondary Endpoints Summary Table

Endpoint	Primary Analysis Method	Sensitivity/Exploratory Analysis
Secondary Endpoints (Continued)		
DAS28-CRP and change from baseline at all measured timepoints	Similar analysis as for SDAI score and change from baseline at all measured timepoints	
CDAI and change from baseline at all measured timepoints	Similar analysis as for SDAI score and change from baseline at all measured timepoints	
SDAI remission (≤ 3.3) at all measured timepoints	Count (percentage) of subjects achieving SDAI remission as defined by SDAI_remission_maintenance detailed in Section 6.5 for the PAS. Chi-squared test comparing etanercept monotherapy vs methotrexate monotherapy Chi-squared test comparing etanercept and methotrexate combination therapy vs methotrexate monotherapy	
Boolean remission at all measured timepoints	Observed count (percentage) of subjects achieving Boolean remission at each Analysis Visit for the PAS. Boolean remission using 28-joint-count, 28-joint-count + feet and ankles, and 66/68 joint count will be assessed. Chi-squared test comparing etanercept monotherapy vs methotrexate monotherapy Chi-squared test comparing etanercept and methotrexate combination therapy vs methotrexate monotherapy	
Disease-Worsening defined as an SDAI > 3.3 and ≤ 11 during two consecutive visits at least 2 weeks apart or SDAI > 3.3 and ≤ 11 on three or more separate visits or SDAI > 11 after randomization	Observed count (percentage) of subjects fulfilling Disease-Worsening criteria at each Analysis Visit for the PAS.	

Table 1. Primary and Secondary Endpoints Summary Table

Endpoint	Primary Analysis Method	Sensitivity/Exploratory Analysis
Secondary Endpoints (Continued)		
Time to Disease-Worsening as an SDAI > 3.3 and ≤ 11 during two consecutive visits at least 2 weeks apart or SDAI > 3.3 and ≤ 11 on three or more separate visits or SDAI > 11 after randomization	Kaplan-Meier curves, estimates, and 95% CIs assessing Time to Disease-Worsening by treatment group for the PAS. Subjects with more than one DW Date will be analyzed using the first DW Date. Subjects who do not experience disease-worsening will be censored at last SDAI assessment date. Log-rank test comparing etanercept monotherapy versus methotrexate monotherapy. Log-rank test comparing etanercept and methotrexate combination therapy versus methotrexate monotherapy.	
Time to recapture observed SDAI remission after starting rescue treatment	Kaplan-Meier curves assessing Time to recapture observed SDAI remission from Rescue Date for the Rescue Analysis Set. Subjects with more than one recapture of SDAI remission will be analyzed using their first recapture date. Subjects who do not recapture SDAI remission are censored at their last SDAI assessment date. Log-rank test comparing etanercept monotherapy versus methotrexate monotherapy. Log-rank test comparing etanercept and methotrexate combination therapy versus methotrexate monotherapy.	Similar analysis as the Primary Analysis Method but using the Disease-Worsening Analysis Set, looking at time to recapture SDAI remission from DW Date.
Observed SDAI remission at Week 48	Observed count (percentage) of subjects achieving SDAI remission as defined by Observed_SDAI_remission as detailed in Section 6.5 at Week 48 for the Rescue Analysis Set.	Similar analysis as the Primary Analysis Method but using the Disease-Worsening Analysis Set.

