## **10. STATISTICAL CONSIDERATIONS**

### **10.1 Study Endpoints, Analysis Sets, and Covariates**

#### **10.1.1 Study Endpoints**

##### **10.1.1.1 Primary Endpoint**

- SDAI remission ( $\leq 3.3$ ) at week 48

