## **10.5 Planned Methods of Analysis**

### **10.5.1 General Considerations**

Baseline demographics and disease characteristics will be summarized descriptively.

Summary descriptive statistics by each treatment group will be provided. For categorical endpoints, the descriptive statistics will contain the frequency and percentage. For continuous endpoints, the descriptive statistics will include the number of observations, mean, standard deviation, median, minimum, maximum and 95% confidence interval.

Non-responder imputation will be employed for the missing values of the primary endpoint. Secondary efficacy endpoints will be summarized using observed cases only. As supportive analysis, the primary endpoint will also be summarized using observed cases.

The statistical test for the primary efficacy endpoint will be two-sided with a significance level of 0.05.

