4.1 Study Endpoints

4.1.1 Primary Endpoint

- SDAI remission (≤ 3.3) at week 48

The primary estimand consists of:

- Target population – patients with a history of moderate to severe rheumatoid arthritis (RA) who are on etanercept and methotrexate combination therapy and who are in very good disease control.
- Endpoint – SDAI remission (SDAI \leq 3.3) at week 48
- Intercurrent events – there are 2 intercurrent events: first, discontinuation of IP before week 48; second, disease-worsening after randomization which triggers initiation of rescue therapy. Treatment effects will be estimated for subjects regardless of whether subjects complete 48 weeks of IP.
- Summary measure – difference in the proportion of subjects achieving SDAI \leq 3.3 (yes/no) at Week 48 on etanercept monotherapy and that of subjects achieving SDAI \leq 3.3 (yes/no) at Week 48 on methotrexate monotherapy.

In summary, the primary estimand is the difference in proportions of subjects in etanercept monotherapy and methotrexate monotherapy maintaining SDAI remission at Week 48 without experiencing disease-worsening on study in adults with a history of moderate to severe RA who have been on etanercept and methotrexate combination therapy and in very good RA disease control, regardless of adherence to treatment and completion of 48 weeks of IP.

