6.2 Primary Endpoint

Primary Endpoint - SDAI remission at week 48

The primary endpoint of SDAI remission is defined as achievement of SDAI \leq 3.3 at Week 48 without fulfilling the definition of disease-worsening during the study.

Primary endpoint of SDAI remission will be defined as follows:

- SDAI_remission_maintenance (\leq 3.3) at Week 48 = 1, if SDAI \leq 3.3 at Week 48 AND subject did not fulfill the definition of disease-worsening during the study;
- SDAI_remission_maintenance (\leq 3.3) at Week 48 = missing, if subject has no Week 48 SDAI value AND subject did not fulfill the definition of disease-worsening during the study;
- SDAI_remission_maintenance (\leq 3.3) at Week 48 = 0, otherwise.

Different statistical methods for addressing missing SDAI remission status are addressed in [Section 11.5](#).

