if SDAI ≤ 3.3 at Analysis Visit k ;
- Observed_SDAI_remission (≤ 3.3) at Analysis Visit $k = \text{missing}$,
if subject has no SDAI value at Analysis Visit k ;
- Observed_SDAI_remission (≤ 3.3) at Analysis Visit $k = 0$,
if SDAI > 3.3 at Analysis Visit k .

Observed SDAI Remission at DW Visit (or Rescue Visit) k

- Observed_SDAI_Remission at DW Visit (or Rescue Visit) $k = 1$,
if SDAI ≤ 3.3 at DW Visit k ;
- Observed_SDAI_remission (≤ 3.3) at DW Visit (or Rescue Visit) $k = \text{missing}$,
if subject has no SDAI value at DW Visit k ;
- Observed_SDAI_remission (≤ 3.3) at DW Visit (or Rescue Visit) $k = 0$,
if SDAI > 3.3 at DW Visit k .

Disease Activity

For a specific timepoint, subjects are classified as having

- SDAI Low Disease Activity (LDA): $3.3 < \text{SDAI} \leq 11$
- SDAI Moderate Disease Activity (MDA): $11 < \text{SDAI} \leq 26$
- SDAI High Disease Activity (HDA): $\text{SDAI} > 26$

Disease-Worsening

During the double-blind treatment period, disease-worsening for the study is defined as:

- $\text{SDAI} > 3.3$ and ≤ 11 on two consecutive visits at least two weeks apart OR
- $\text{SDAI} > 3.3$ and ≤ 11 on three or more separate visits OR
- $\text{SDAI} > 11$ at anytime

Disease-Worsening may be assessed at a regularly scheduled visit or at an unscheduled Disease Assessment visit. Subjects will remain on study and complete all study visits.

Disease Activity Score using the erythrocyte sedimentation rate formula (DAS28-ESR)

A modified composite index that was designed to measure disease activity in subjects using the number of tender and swollen joints based upon a 28-joint count, ESR in mm/hr, and a 100 mm visual analog scale measuring the subject's general health. A higher score represents worse disease.

Details of the scoring algorithm are described in [Appendix A](#).

Disease Activity Score using the C-reactive protein formula (DAS28-CRP)

A composite index that was designed to measure disease activity in subjects using the number of tender and swollen joints based upon a 28-joint count, CRP in mg/L, and a 100 mm visual analog scale measuring the subject's general health. A higher score represents worse disease.

Details of the scoring algorithm are described in [Appendix A](#).

DAS28-ESR remission

Subjects are classified as achieving DAS28-ESR remission at a specific timepoint if their DAS28-ESR < 2.6 at that timepoint. Specifically, let DAS28ESR_remission be defined as follows:

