11.5.1.2 Sensitivity/Exploratory Analyses of Primary Estimand

SDAI remission at Week 48 will be tested using a chi-squared test at significance level of 0.05 using observed cases only.

In addition, multiple-imputation will be implemented to impute SDAI values when missing for randomized subjects. SDAI values after rescue are also set to missing and imputed in this analysis. The composite SDAI values will be imputed rather than its components. A chi-squared test will compare the resulting values under the etanercept monotherapy arm and the methotrexate monotherapy arm.

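### The observed-case analysis of the primary endpoint uses a variable that ignores disease-worsening, so remission regained on rescue counts as success for the randomized arm

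*SAP*

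**What the plan says.** The primary estimand in SAP 4.1.1 concerns subjects "maintaining SDAI remission at Week 48 without experiencing disease-worsening on study". Section 6.2 defines the endpoint variable, `SDAI_remission_maintenance`, as SDAI of 3.3 or less at Week 48 "without fulfilling the definition of disease-worsening during the study". Under 6.2 a subject's status is missing only if there is no Week 48 SDAI and the subject never met disease-worsening.

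SAP 11.5.1.2, whose heading names sensitivity and exploratory analyses of the primary estimand, plans two further analyses. The first is "SDAI remission at Week 48 will be tested using a chi-squared test at significance level of 0.05 using observed cases only"; the sentence does not name the variable. The second is multiple imputation, for which "SDAI values after rescue are also set to missing and imputed in this analysis".

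Table 1 does name the variable. In the sensitivity/exploratory cell of the primary-endpoint row it specifies "Observed_SDAI_remission using as observed approach as detailed in Section 6.5 (missing data will be excluded", and the combination-versus-methotrexate row has the same cell. In Section 6.5 `Observed_SDAI_remission` is 1 or 0 according to the SDAI at the visit, and missing only "if subject has no SDAI value at Analysis Visit" k. It has no disease-worsening or rescue condition.

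The protocol leaves the choice open. Section 10.5.1 says "As supportive analysis, the primary endpoint will also be summarized using observed cases". The endpoint in 10.1.1.1 has no disease-worsening condition, but 10.5.2 makes subjects rescued for disease worsening non-responders. SAP Section 12 discloses added exploratory endpoints and points to 4.1.4, which lists the observed variable, but it does not say that this variable enters the primary-endpoint row.

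**The concern.** An observed-case analysis placed beside non-responder imputation and multiple imputation will be read as a check on missing data: same endpoint, different treatment of unknown status. Here the endpoint changes too.

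Subjects who worsen are to start etanercept plus methotrexate and complete all visits (Protocol 3.1.1, 3.1.2, 7.2.7), and they are analysed in the arm to which they were randomized (SAP 7.1). Two things follow. A methotrexate-arm subject who worsened, was rescued with the combination and has SDAI of 3.3 or less at Week 48 becomes a methotrexate success. A subject who worsened and has no Week 48 SDAI is a known failure under 6.2 but is excluded here.

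A weaker or stronger observed-case result could therefore be taken as evidence about missing data when it reflects how well rescue works. The two analyses under one heading also treat post-rescue values in opposite ways.

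**Working it through.** **1. The two variables, subject by subject**

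| Subject at Week 48 | Section 6.2 variable | Section 6.5 observed variable |
|---|---|---|
| No disease-worsening, SDAI ≤ 3.3 | 1 | 1 |
| No disease-worsening, SDAI > 3.3 | 0 | 0 |
| No disease-worsening, no SDAI | missing | missing |
| Disease-worsening, SDAI ≤ 3.3 | 0 | **1** |
| Disease-worsening, SDAI > 3.3 | 0 | 0 |
| Disease-worsening, no SDAI | 0 | **missing** |

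The variables differ in the fourth and sixth rows. SAP 11.5.2 uses the same observed variable to measure recapture of remission in the Rescue and Disease-Worsening sets, which confirms that it credits post-rescue remission.

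**2. The plan's own figure**

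Inputs from SAP 3.2: 72% versus 50%, two-sided alpha 0.05, power 90%, 100 per arm. With pooled variance and mean rate 0.61:

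n = [1.960·√(2·0.61·0.39) + 1.282·√(0.72·0.28 + 0.50·0.50)]² / 0.22² = 101.2, so 102 per arm.

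The unpooled form gives 98.04. Power at 100 per arm is 89.7% by normal approximation and 89.8% by exact binomial enumeration. The stated 100 per arm is reproduced.

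**3. Effect of crediting remission after rescue, no missing data**

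Let r be the share of primary non-responders in observed remission at Week 48 after rescue. This is an assumption, because neither document gives such a rate. The observed rate in an arm is p + (1 − p)·r. With equal r the difference is 22·(1 − r) points. Power is exact, uncorrected two-sided chi-square, 100 per arm.

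| r etanercept | r methotrexate | Etanercept | Methotrexate | Difference (points) | Power |
|---|---|---|---|---|---|
| 0 | 0 | 72.0% | 50.0% | 22.0 | 90% |
| 0.1 | 0.1 | 74.8% | 55.0% | 19.8 | 84% |
| 0.3 | 0.3 | 80.4% | 65.0% | 15.4 | 69% |
| 0.5 | 0.5 | 86.0% | 75.0% | 11.0 | 51% |
| 0.3 | 0.5 | 80.4% | 75.0% | 5.4 | 15% |
| 0.5 | 0.2 | 86.0% | 60.0% | 26.0 | 99% |

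**4. Both effects together**

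Assume 10 per arm lack a Week 48 SDAI, 5 of them after disease-worsening, and that all 10 are primary non-responders. The other non-responders number 28 − 10 = 18 on etanercept and 50 − 10 = 40 on methotrexate.

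- Table 1 variable, half of the others in observed remission: (72 + 9)/90 versus (50 + 20)/90 = 90.0% versus 77.8%, 12.2 points, power 61%.
- Table 1 variable, share 0.3: (72 + 5.4)/90 versus (50 + 12)/90 = 86.0% versus 68.9%, 17.1 points, power 79%.
- Table 1 variable, share 0: 72/90 versus 50/90 = 80.0% versus 55.6%, 24.4 points.
- Section 6.2 variable, excluding only the 5 with missing status, at any recapture share: 72/95 versus 50/95 = 75.8% versus 52.6%, 23.2 points, power 92%.

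**5. Combination row**

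Assume 78.3% to 86.1% on the combination (the earlier-study rates in SAP 3.2; n = 50) versus 50% on methotrexate (n = 100). With r = 0.5 in both arms the difference falls from 28.3–36.1 to 14.2–18.1 points, and normal-approximation power from 94–99.7% to 53–80%.

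**The case against.** The strongest reply is that this is a mismatch between text and table. Section 11.5.1.2 names no variable, and 6.2 refers to 11.5 for the handling of missing remission status, so the text can be read as already applying observed cases to the 6.2 variable. That reading is possible, but Table 1 is the only place that names a variable, and it names the other one in both rows.

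Second, the heading says exploratory as well as sensitivity, and Week 48 remission regardless of rescue is a legitimate question that fits the protocol's bare endpoint. That is true, but it is a different estimand from the one the heading names, and it already has its own place in 4.1.4 and 11.5.3.

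Third, other planned outputs help. If denominators are reported by arm, the correct two-by-two table could be rebuilt from the primary analysis, the disease-worsening counts and the Week 48 summary in the Disease-Worsening set. Multiple imputation is a second missing-data analysis that does not credit post-rescue values, and the disease-worsening date definition in 6.1 suggests that it keeps the composite endpoint. This softens the consequence, but a table that a reader could rebuild is not a planned test.

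Fourth, the size depends on assumed recapture and has no fixed direction. Protocol 2.4 speaks only of a return to low disease activity, not remission. In step 4 the lost denominator alone moves the difference by only 24.4 − 23.2 = 1.2 points; the rest comes from recapture. This stands, and the figures are illustrations only.

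Fifth, rescue in the combination arm continues the assigned treatments, so remission regained there reflects no change of treatment. This also stands, but the methotrexate arm in that comparison is still affected.

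**Conclusion.** The concern holds and should be fixed. As Table 1 is written, the observed-case analysis changes both who is excluded and what counts as success, so on its own it cannot show whether the primary result is robust to missing data. No planned test clearly applies observed cases to the Section 6.2 variable. That conclusion rests on the text and needs no assumption.

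The size does rest on assumptions about recapture and missing data. In the scenarios above the planned 22-point difference becomes anything from 5.4 to 26.0 points. The primary non-responder analysis, its alpha, the sample size, SDAI remission by visit and time to disease-worsening are unaffected.

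**What to change.** 1. In SAP 11.5.1.2 and in both Table 1 rows, specify the observed-case analysis on `SDAI_remission_maintenance` (Section 6.2), excluding only subjects whose status is missing under that definition. Subjects who met disease-worsening stay at 0, and the analysis then differs from the primary one only in how missing status is handled.
2. Keep `Observed_SDAI_remission` as the separate exploratory endpoint it already is in 4.1.4 and 11.5.3. Label it as including post-rescue values and not as a sensitivity analysis of the primary estimand.

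The cost is two table cells, one sentence and one label. Both variables are already derived, and no new data are needed.
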